Appendix A

		
Measured 90 days prior to drug initiation in any diagnosis position in inpatient and outpatient care setting:
 
Any stroke ICD-9 Dx: 430.xx, 431.xx, 433.xx, 434.xx, 436.xx
 
TIA 435.xx
	
Paterno, Elisabetta et al. "Cardiovascular outcomes associated with canagliflozin versus other non-gliflozin antidiabetic drugs: population based cohort study." BMJ 2018;360:k119 http://dx.doi.org/10.1136/bmj.k119
 
Paterno, Elisabetta et al. "Empagliflozin and the Risk of Heart Failure Hospitalization in Routine Clinical Care: A First Analysis from the Empagliflozin Comparative Effectiveness and Safety (EMPRISE) Study." Circulation. 2019 Apr 8. doi: 10.1161/CIRCULATIONAHA.118.039177

		13) Stroke or TIA ≤ 3 months prior to visit 1 (screening).	

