	The primary outcome is the time to the first occurrence of CV death, non-fatal myocardial infarction (MI) or non-fatal stroke—the so-called 3-point major adverse CV events (3P-MACE) composite outcome.	
Measured 1 days after drug initiation in diagnosis position specified below and inpatient care setting:
 
Inpatient mortality/MI/Stroke –
 
For MI Any diagnosis position in inpatient care setting ICD-9 Dx 410.X (acute myocardial infarction) excluding 410.x2 (subsequent episode of care)
 
For stroke Primary diagnosis position in inpatient care setting ICD-9 discharge diagnosis: 430.xx Subarachnoid hemorrhage (SAH) 431.xx Intracerebral hemorrhage (ICH) 433.x1 Occlusion and stenosis of precerebral arteries with cerebral infarction 434.xx (excluding 434.x0) Occlusion and stenosis of cerebral arteries with cerebral infarction 436.x Acute, but ill-defined cerebrovascular events
 
Mortality- See Mortality Sheet.
	
For MI:
 
►PPV 94% in Medicare claims data [Kiyota Y, Schneeweiss S, Glynn RJ, Cannuscio CC, Avorn J, Solomon DH. Accuracy of Medicare claims-based diagnosis of acute myocardial infarction: estimating positive predictive value on the basis of review of hospital records. American heart journal 2004;148:99-104.]
 
►PPV 88.4% in commercially-insured population [Wahl PM, Rodgers K, Schneeweiss S, et al. Validation of claims-based diagnostic and procedure codes for cardiovascular and gastrointestinal serious adverse events in a commercially-insured population. Pharmacoepidemiology and Drug Safety 2010;19:596-603.]
 
For stroke:
 
PPV of 85% or higher for ischemic stroke PPV ranging from 80% to 98% for hemorrhagic stroke
 
 
 
	Can't be measured in claims but not important for the analysis
	INCLUSION CRITERIA			

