Appendix A

	6) Body Mass Index (BMI) ≥ 45 kg/m ² at visit 1 (screening).	Measured 180 days prior to drug initiation any diagnosis position in inpatient or outpatient care setting: Excluding patients with ICD-9 Diagnosis Code (any position) is any of: {"278.01"} 278.01-MORBID OBESITY	
	7) Signed and dated written informed consent by date of visit 1 (screening) in accordance with GCP and local legislation prior to any study related procedure.	N/A	-
	8) High risk of CV events (I and/or II):		
I	Albuminuria (UACR ≥ 30 mg/g creatinine or ≥ 30 µg/min [microgram albumin per minute] or ≥ 30 mg/24 h [milligram albumin per 24 hours] in two out of three unrelated spot urine or timed samples in the last 24 months prior to randomization)* AND previous macrovascular disease, defined as either one or more:		
Ia	Confirmed history of MI (>2 months prior to Visit 1)	Measured from the start of all available data to on the date of drug initiation with diagnosis/procedure position and care setting as noted below:	

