Ic	High-risk single-vessel coronary artery disease, defined as the presence of ≥ 50% narrowing of the luminal diameter of one major coronary artery by coronary angiography, MRI angiography or CT angiography in patients not revascularized: AND at least one of the following: • A positive non invasive stress test, confirmed by either: o a positive ECG exercise tolerance test in patients without left bundle branch block, Wolff-Parkinson-White syndrome, left ventricular hypertrophy with repolarization abnormality, or paced ventricular rhythm, atrial fibrillation in case of abnormal ST-T segments; o a positive stress echocardiogram showing induced regional systolic wall motion abnormalities; o a positive nuclear myocardial perfusion imaging stress test showing stress- induced reversible perfusion abnormality; o a positive cardiac stress perfusion MRI showing a stress induced perfusion defect; • Patient discharged from hospital with a documented diagnosis of unstable angina pectoris between 2 and 12 months prior to visit 1 (screening).		
Id	History of ischemic or haemorrhagic stroke (>3 months prior to visit 1)	Measured from the start of all available data to on the date of drug initiation in any diagnosis position and procedure position in inpatient or outpatient care setting: Any stroke ICD-9 Dx: 430.xx, 431.xx, 433.xx, 434.xx, 436.xx	We including anytime prior to drug initiation here, but then any patients with any stroke within last 3 months are excluded due to the last exclusion criteria.

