Ie	Presence of carotid artery disease (symptomatic or not) documented by either: o imaging techniques with at least one lesion estimated to be ≥50% narrowing of the luminal diameter; o prior percutaneous or surgical carotid revascularization.	Measured from the start of all available data to on the date of drug initiation in any diagnosis position and procedure position in inpatient or outpatient care setting: Carotid artery disease ICD-9 433.10 : Occlusion and stenosis of carotid artery without mention of cerebral infarction. ICD-10-CM I65.29 Occlusion and stenosis of unspecified carotid artery	Patorno, Elisabetta et al. "Cardiovascular outcomes associated with canagliflozin versus other non-gliflozin antidiabetic drugs: population based cohort study." BMJ 2018;360:k119 http://dx.doi.org/10.1136/bmj.k119 Patorno, Elisabetta et al. "Empagliflozin and the Risk of Heart Failure Hospitalization in Routine Clinical Care: A First Analysis from the Empagliflozin Comparative Effectiveness and Safety (EMPRISE) Study." Circulation . 2019 Apr 8. doi: 10.1161/CIRCULATIONAHA.118.039177

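### As printed, Exclusion 13 (stroke or TIA within 90 days) also removes patients coded only with arterial stenosis without infarction, including 433.10, the code that Inclusion 8 Ie uses to admit carotid disease

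*Combined protocol and SAP*

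**What the plan says.** All the passages are in Appendix A.

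- **Exclusion 13.** The trial criterion is stroke or TIA within three months of screening. The claims version is "Any stroke ICD-9 Dx: 430.xx, 431.xx, 433.xx, 434.xx, 436.xx" together with TIA 435.xx, looked for over 90 days before initiation, in any diagnosis position, inpatient and outpatient.
- **Inclusion 8 Ie.** The trial criterion begins "Presence of carotid artery disease (symptomatic or not) documented by either", followed by imaging evidence or "prior percutaneous or surgical carotid revascularization". The claims version uses all available history up to the initiation date and prints ICD-9 433.10, described as "Occlusion and stenosis of carotid artery without mention of cerebral infarction", and ICD-10-CM I65.29. It prints no procedure code.
- **Inclusion 8 Id (prior stroke).** It prints the same stroke list over all available history. Its note says that "any patients with any stroke within last 3 months are excluded due to the last exclusion criteria".
- **Primary outcome.** Stroke is limited to infarction and haemorrhage codes plus 436: "433.x1 Occlusion and stenosis of precerebral arteries with cerebral infarction" and "434.xx (excluding 434.x0) Occlusion and stenosis of cerebral arteries with cerebral infarction", with 430, 431 and 436, in the primary inpatient position.
- **Inclusion 8 If.** The trial criterion concerns limb revascularization, amputation and limb artery stenosis. The printed codes are ICD-9 procedure 39.28 and ten ICD-10 codes for carotid-to-intracranial bypass.

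**The concern.** Code 433.10 falls inside 433.xx. As printed, one outpatient 433.10 claim in the last 90 days both qualifies a patient under Ie and removes that patient as a recent stroke. The trial's Exclusion 13 names stroke and TIA only, and the appendix's own label for 433.10 says that no infarction is mentioned. The other no-infarction codes under 433 and 434 are caught in the same way. The outcome definition shows that the study team does separate these codes where it wants to. The Id note accepts the overlap with Exclusion 13 for stroke, but no note covers stenosis without infarction.

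What is at stake is an eligibility rule that misclassifies some patients if followed as written, in a study whose Section 5.2.2 aims to track the trial criteria closely. A second programmer working from Appendix A could not tell which cohort was meant.

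**Working it through.** **1. Reproduce the flowchart step (Section 5.3).**
- Optum: 125,291 − 2,292 = 122,999; 2,292/125,291 = 1.83%.
- MarketScan: 124,874 − 1,981 = 122,893; 1,981/124,874 = 1.59%.
- Medicare: 407,920 − 7,081 = 400,839; 7,081/407,920 = 1.74%.
- Total: 2,292 + 1,981 + 7,081 = 11,354 of 658,085 = 1.73%.

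All three results match the printed cohorts. The 11,354 include true strokes and TIAs. The plan does not count those removed on a no-infarction code alone, so the range is 0 to 11,354 (0 to 1.7%).

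**2. Effect on power.** Inputs are the event counts in Section 10. The formula is power = Φ(√d/2 × ln 1.3 − 1.96).
- Optum, d = 2 × 8,880 × 0.01655 = 293.928: 0.6137, as printed.
- MarketScan, d = 2 × 8,716 × 0.0187 = 325.9784: 0.6586, as printed.

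Now restore every removed patient and assume that matched events rise in proportion, which is the most favourable case.
- Optum: 293.928 × 125,291/122,999 = 299.4 events; power 0.6217, a gain of 0.008.
- MarketScan: 325.9784 × 124,874/122,893 = 331.2 events; power 0.6655, a gain of 0.007.
- Medicare and pooled power stay above 0.999.

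**3. Was the printed list the one that was run?** Appendix B, Table 1 (unmatched, after all exclusions) has a row for any stroke. Referent plus exposed:
- Optum: 5,024 + 347 = 5,371.
- MarketScan: 4,490 + 355 = 4,845.
- Medicare: 20,639 + 1,835 = 22,474.
- Total: 32,690 of 645,193 (5.07%), and 32,690/11,354 = 2.9.

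The row states no window. Assume that it covers the 180-day baseline that Section 6.2 gives for the comorbidity index, and that the printed list was run. Then essentially all 32,690 would carry stroke codes only in the earlier half of that window, against 11,354 removed for the later half with TIA included. That is hard to reconcile. A narrower exclusion list as run would explain it; so would a longer covariate window. The documents do not settle which.

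**4. The If row.** Ie names carotid revascularization and prints no procedure code; If, on limb disease, prints only carotid bypass codes. A cell placed in the wrong row would explain both. A blank or misplaced cell does not show that a criterion was skipped: Inclusion 1 prints no code, yet the flowchart removed 18,341 + 37,618 + 10,507 = 66,466 patients on it.

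**The case against.** **Admitting on all history and then removing recent cases is how the appendix works.** Ib admits 410.xx–414.xx at any time, and Exclusion 12 removes 411.xx within 60 days. So a shared code is not in itself a contradiction, and patients with 433.10 coded only before the 90-day window stay in. This stands, but it does not answer the point. Exclusion 12 is about acute coronary syndrome, and 411.xx is the code it prints for that condition. By the appendix's own label, 433.10 is neither stroke nor TIA.

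**An exclusion may fairly be more sensitive than an outcome.** The outcome list is built for specificity and cites predictive values. Table 1 labels ischemic stroke as with and without mention of infarction, so the broad definition is used knowingly elsewhere, and the Exclusion 13 row cites two published studies. The breadth may therefore be deliberate. Even so, nothing printed says how it fits with Ie.

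**The full lists sit in an external folder.** True, and the ICD-10 list for Exclusion 13 is not printed, so the conflict is shown for ICD-9 only. The ICD-9 lists are printed, however, and they conflict.

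A reader might infer three stronger things that the documents do not support:
- That 11,354 patients were wrongly removed. This is a ceiling, and the true number could be zero.
- That the hazard ratio is biased. The rule applies to both treatment groups, and no differential effect is shown.
- That patients with limb artery disease alone were lost. The If codes look misplaced, and Table 1 carries a peripheral vascular disease covariate.

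**Conclusion.** The point holds for Exclusion 13 as printed in ICD-9: it removes patients whose only code in the last 90 days is stenosis or occlusion without infarction, which Ie uses, through 433.10, to admit carotid disease. The effect is small: 0 to 11,354 of 658,085 patients (0 to 1.7%). The power gain of at most 0.008 assumes that events scale with the restored patients. The gain in match to the trial is also limited. Criterion I requires albuminuria "AND previous macrovascular disease, defined as either one or more", and no albuminuria code is printed. Whether anyone was in fact wrongly removed depends on the executed list, and the Table 1 counts leave room for a narrower one. The If mismatch is a query about the print only. The main gain is a correct and reproducible definition.

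**What to change.** 1. Check the stroke list that was executed for Exclusion 13, in ICD-9 and ICD-10.
2. If it matches the print and the breadth was not intended, restrict the stroke codes to those of the primary outcome: 430, 431, 433.x1, 434.xx excluding 434.x0, and 436, with ICD-10 equivalents. Keep TIA 435, then re-run the flowchart and the matching.
3. If a narrower list was run, correct Appendix A to show it.
4. If the broad list is deliberate, say so in one sentence and state how it fits with Ie.
5. Leave Id unchanged for now. Narrowing it could drop patients who qualify only through other no-infarction codes under 433 or 434, and they have not been counted. Code 433.10 itself makes no difference there, since Ie admits it over the same history.
6. Separately, confirm the executed limb artery list, correct the If row, and move the carotid bypass codes to Ie if that is where they belong.

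The cost is a check of stored lists and an edit to Appendix A. Only the second case needs a cohort re-run, and no new data are required. The date fields in Sections 12 and 13 are blank, so on the face of the document this can be done before any outcome comparison.

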Appendix A

Trial ID	
Trial Name (with web links)	CARMELINA
NCT	NCT01897532
Trial category	5a- Successful NI with label change
Therapeutic Area	Endocrinology
RCT Category	Secondary indication
Brand Name	
Generic Name	Linagliptin
Sponsor	Boehringer Ingelheim
Year	2019
Measurable endpoint	Composite of Cardiovascular Death, Non-fatal Myocardial Infarction, or Non-fatal Stroke
Exposure	Linagliptin
Comparator	Placebo
Population	
Trial finding	1.02 (95% CI 0.89-1.17)
No. of Patients	6979
Non-inferiority margin	1.3
Assay Sens. Endpoint	
Assay Sens. Finding	
Power	Power- 0.90. Assuming a HR of 1.0, to demonstrate non-inferiority of linagliptin versus placebo within the pre-specified non-inferiority margin of 1.3 at a one-sided α -level of 2.5%.
Blinding	
Statistical Method	

Appendix A

Mortality- Dependent on data source.

1. All-cause mortality / inpatient mortality

Identified using the vital status file-

Medicare

Identified using the discharge status codes-

Optum-

- 20 = EXPIRED
- 21 = EXPIRED TO BE DEFINED AT STATE LEVEL
- 22 = EXPIRED TO BE DEFINED AT STATE LEVEL
- 23 = EXPIRED TO BE DEFINED AT STATE LEVEL
- 24 = EXPIRED TO BE DEFINED AT STATE LEVEL
- 25 = EXPIRED TO BE DEFINED AT STATE LEVEL
- 26 = EXPIRED TO BE DEFINED AT STATE LEVEL
- 27 = EXPIRED TO BE DEFINED AT STATE LEVEL
- 28 = EXPIRED TO BE DEFINED AT STATE LEVEL
- 29 = EXPIRED TO BE DEFINED AT STATE LEVEL
- 40 = EXPIRED AT HOME (HOSPICE)
- 41 = EXPIRED IN A MEDICAL FACILITY (HOSPICE)
- 42 = EXPIRED - PLACE UNKNOWN (HOSPICE)

Truven-

- 20 - Died
- 22 - Died
- 23 - Died
- 24 - Died
- 25 - Died
- 26 - Died
- 27 - Died
- 28 - Died
- 29 - Died
- 40 - Other died status or Expired at home (Hospice claims only) (depends on year)
- 41 - Other died status or Expired in medical facility (Hospice claims only) (depends on year)

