6.3.1 Outcome variables

Effectiveness outcomes of interest (definitions provided in **Appendix A**):

- **Primary outcome:** 3-point major adverse cardiovascular events (MACE), i.e., non-fatal myocardial infarction, non-fatal stroke, or CV mortality
- Secondary outcomes: Individual MACE components:
 - Hospital admission for MI (for purposes of this individual component, fatal MI is included)
 - Hospital admission for stroke (for purposes of this individual component, fatal stroke is included)
 - All-cause mortality/CV mortality:
 - All-cause inpatient mortality identified using discharge status codes will be used as a proxy for “CV mortality” in commercial databases
 - Information on CV mortality through data linkage with the National Death Index (NDI) will only become available at a later date for Medicare and will be used in secondary analyses.

Control outcomes of interest (control outcomes only serve to assess aspects of study validity but are not further interpreted):

1. End Stage Renal Disease (we expect to see no association; Rosenstock et al., 2019)

Control outcome definitions

Outcome	Definition	Comments
Control Outcomes		
End Stage Renal Disease (ESRD)	
ESRD with dialysis, defined as:
 
An ICD9 diagnosis (inpatient or outpatient) for ESRD:
 
 ○ 585.5x, Chronic kidney disease, Stage V (for ESRD with no mention of dialysis) ○ 585.6x, End stage renal disease (for ESRD with dialysis) 
AND an ICD9 procedural codes for dialysis (=index date):
 
 ○ 39.95, Hemodialysis ○ 54.98, Peritoneal dialysis 
AND an additional procedural code for dialysis or physician provider code indicating dialysis procedure or ESRD-related activity within two time windows 31-60 and 61-90 days from index date. For patients who die prior to 61 days (31 days), the second (second and first) confirmation requirement(s) can be dropped. This ensures the inclusion of patients with true ESRD outcomes who die early (high early mortality) as well as early withdrawals from dialysis (which lead to high fatality within days or weeks).
	
Note- The corresponding ICD-10 codes will be used also

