Appendix A

- 42 - Other died status or Expired - place unknown (Hospice claims only) (depends on year)
- 21 - Died or Disch./Transf. to court/law enforcement (depends on year)

2. CV mortality

Information on CV mortality through data linkage with the National Death Index (NDI) will be available for Medicare at a later date. We will conduct secondary analyses using CV mortality at that time.

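### The death component of the primary composite differs by database, and the Appendix A code lists do not match the inpatient mortality that the plan describes

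*Combined protocol and SAP*

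**What the plan says.** Section 6.3.1 names the primary outcome as "3-point major adverse cardiovascular events (MACE), i.e., non-fatal myocardial infarction, non-fatal stroke, or CV mortality". For the commercial databases it adds: "All-cause inpatient mortality identified using discharge status codes will be used as a proxy for" CV mortality. It gives no death rule for Medicare in the primary composite. Cause of death from the National Death Index will come later, for Medicare only, and is kept for secondary analyses.

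The primary-outcome row of Appendix A labels the claims version "Inpatient mortality/MI/Stroke", with no database qualifier. It sets the measurement as "Measured 1 days after drug initiation in diagnosis position specified below and inpatient care setting", and for death it says "Mortality- See Mortality Sheet".

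That sheet says the rule depends on the data source, and its first heading joins all-cause and inpatient mortality. Under that heading:

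- Medicare deaths are "Identified using the vital status file". No place or cause restriction follows.
- Optum deaths come from discharge status codes, including "40 = EXPIRED AT HOME (HOSPICE"), 41 (hospice, in a medical facility) and 42 (hospice, place unknown).
- MarketScan (headed Truven) deaths come from a similar list. Codes 40 to 42 mean either another died status or a hospice death, depending on year. The list also contains "21 - Died or Disch./Transf. to court/law enforcement (depends on year").

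**The concern.** Three statements of one endpoint component disagree. A programmer working from the primary-outcome row would build a Medicare composite with in-hospital death. One working from the Mortality sheet would build it with any death anywhere. In the commercial databases, a hospice death at home is not an inpatient death, and a transfer to law enforcement is not a death.

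The pooled analysis would then combine composites with different content. The 1.3 margin in sections 1.2 to 1.4 belongs to a composite whose fatal part is CV death. Deaths unrelated to treatment, or live discharges counted as deaths, add events with a ratio near 1. In a superiority comparison that costs power. In a non-inferiority comparison it makes the claim easier to reach.

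**Working it through.** **The definitions side by side**

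| Database | Section 6.3.1 | Primary-outcome row | Mortality sheet |
|---|---|---|---|
| Medicare | CV mortality; no operational rule | Inpatient death | Vital status file, unrestricted |
| Optum | All-cause inpatient death | Inpatient death | Status codes, including hospice death at home (40) and place unknown (42) |
| MarketScan | All-cause inpatient death | Inpatient death | As Optum, with 40 to 42 varying by year, plus code 21, a live transfer in some years |

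For Medicare the conflict is between the outcome row and the sheet. For the commercial databases the sheet conflicts with both the row and section 6.3.1. Code 21 is a problem in MarketScan only, because the Optum list labels it as expired.

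**The plan's own figures (section 10)**

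Events = 2 × patients per arm × risk per 1,000 / 1,000.

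- Optum: 2 × 8,880 × 16.55 / 1,000 = 293.928
- MarketScan: 2 × 8,716 × 18.7 / 1,000 = 325.978
- Medicare: 2 × 33,319 × 42.47 / 1,000 = 2,830.116

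Power = Φ(√(events/4) × ln 1.3 − 1.96) gives 0.6137, 0.6586 and 0.9999997. All three match the stated values.

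**Weight of each rule**

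The sum is 293.928 + 325.978 + 2,830.116 = 3,450.02. I use this sum because the stated pooled count of 2,638 is below the Medicare count alone. It rests on the unweighted mean of the three risks, (16.55 + 18.7 + 42.47)/3 = 25.91.

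- Medicare: 2,830.116 / 3,450.02 = 82.0%
- MarketScan: 325.978 / 3,450.02 = 9.4%, which caps what code 21 can affect

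**How far death could matter**

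The censoring table in section 9 gives 1,704 deaths among 101,830 matched patients, not split by database. 1,704 / 3,450 = 49.4%. This is an upper bound on the share of primary events that are deaths, because that run used a dummy outcome and some deaths may follow an MI or stroke.

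If a share f of events is unrelated to treatment (hazard ratio 1) and the true ratio for the rest is 1.30, the observed ratio is roughly 1.30(1 − f) + f = 1.30 − 0.30f. The documents place f only between 0 and 0.494, so the result lies between 1.30 and 1.15. That range is too wide to serve as an estimate.

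**Power of stricter versions**

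In the extreme case, all 1,704 deaths are first events and all are removed.

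- Pooled: 3,450 − 1,704 = 1,746 events, power 0.9998
- Medicare alone, with every death assigned to it: 2,830 − 1,704 = 1,126 events, power 0.993

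**The case against.** Much of the variation is disclosed. The outcome row hands death over to the Mortality sheet, the sheet says the rule depends on source, and section 6.3.1 confines the inpatient proxy to commercial data. So the Medicare vital status file does not contradict section 6.3.1. This stands, and it narrows the Medicare conflict to the unqualified label in the outcome row. It does not give a reader the Medicare rule where the primary outcome is defined.

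The hospice codes may also contribute little if the inpatient care setting in the outcome row filters the claims first. That is possible, but the sheet does not say so.

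Hospital MI and hospital stroke are already secondary outcomes, and CV mortality is planned for Medicare. These help, but no non-inferiority comparison of a composite free of the death proxy is planned.

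A reader might infer a specific false-claim rate. Take all 1,704 deaths as first events, suppose 20%, 40% or 60% are non-CV with ratio 1, and use a standard error of √(4/3,450) = 0.034. A true ratio of 1.30 then appears as 1.27, 1.24 or 1.21, and the chance of concluding non-inferiority rises from 2.5% to about 10%, 28% or 55%. The documents do not support these as estimates. The non-CV share has no source and the death count is an upper bound. The ratio of 1 for such deaths is also assumed: section 9 shows 929 referent and 775 exposed deaths with unequal follow-up, which settles nothing. The calculation also concerns cause of death, and restricting place of death would not remove non-CV deaths in hospital.

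A reader might also infer that Medicare should switch to in-hospital death in the primary. That would lose out-of-hospital CV deaths, which belong to the target endpoint, so the case for it is not made.

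**Conclusion.** The point holds as a mismatch of definitions in the primary endpoint. The death rule differs by database, the Medicare rule as written is wider than the label in the outcome row, both commercial lists reach beyond inpatient death, and MarketScan code 21 lacks a year limit. That Medicare counts every death is the natural reading of an unrestricted vital status file; the plan does not say it in those words.

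It matters because Medicare carries 82% of expected events, and because dilution by unrelated deaths favours non-inferiority. The direction assumes that those deaths have a ratio near 1. The documents do not fix the size. The code 21 problem is confined to a database with 9.4% of events. Medicare's risk is 2.57 times Optum's (42.47/16.55), but older age also contributes, so the gap cannot be credited to the death rule.

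**What to change.** 1. Count MarketScan code 21 only in years when it means death, and list those years.
2. Restrict the commercial death component to inpatient claims, so that hospice-only uses of codes 40 to 42 do not count. Otherwise, change the wording in section 6.3.1 and the primary-outcome row to admit them.
3. If the vital status file is kept for Medicare, say in section 6.3.1 and the outcome row that the Medicare component is all-cause death in any place.
4. Pre-specify two sensitivity analyses against the same 1.3 margin: an MI-or-stroke composite in all three databases, and a Medicare composite with in-hospital death only. State that deaths not counted as events are censored under section 6.3.2.

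The cost is code-list edits, a little extra analysis on data already held, and slightly fewer commercial events. Power for both sensitivity analyses stays above 0.99 even in the extreme case. The in-hospital version misses out-of-hospital CV deaths, so it belongs beside the primary and should not replace it. Section 13 shows no run date, so in this version the changes can still precede the comparative analysis.
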